11.3 Method for Assigning Subjects to Treatment Groups

Not applicable

11.4 Preparation and Administration of Study Drug

Doses will be taken orally with approximately 8 oz. of water. Study drug should be taken at approximately the same times of day. Study drug should be swallowed whole and not crushed, chewed, or dissolved in water.

Missed doses (outside of a 4 hour dosing window) should be skipped and not administered as a double dose at the next administration. Subjects who vomit their dose should be instructed not to make up that dose. Doses that are vomited should not be replaced.

11.5 Subject Compliance Monitoring

Subject compliance will be monitored with the aid of a “Patient Pill Diary” (Appendix D) which will be reviewed by the study team at each visit. Subjects who are non-compliant with protocol schedule or filling out the pill diary will be removed from the study at the discretion of the study investigator.

11.6 Packaging

Ruxolitinib tablets (5 mg) are manufactured, packaged, and labeled according to GMP and GCP at the following address:

DSM Pharmaceuticals, Inc.
Greenville, NC 27834

11.7 Blinding of Study Drug

Not applicable

11.8 Receiving, Storage, Dispensing and Return

11.8.1 Receipt of Drug Supplies

Upon receipt of the of the study treatment supplies, an inventory must be performed and a drug receipt log filled out and signed by the person accepting the shipment. It is important that the designated study staff counts and verifies that the shipment contains all the items noted in the shipment inventory. Any damaged or unusable study drug in a given shipment (active drug or comparator) will be documented in the study files. The investigator must notify agent manufacturer of any damaged or unusable study treatments that were supplied to the investigator's site.

11.8.2 Storage

Ruxolitinib tablets should be stored at room temperature or as described in detail in the current Investigator's Brochure. Subjects should be requested to store the study drug at the recommended storage conditions noted on the label.

11.8.3 Dispensing of Study Drug

Regular study drug reconciliation will be performed to document drug assigned, drug consumed, and drug remaining. This reconciliation will be logged on the drug reconciliation form, and signed and dated by the study team.

11.8.4 Return or Destruction of Study Drug

At the completion of the study, there will be a final reconciliation of drug shipped, drug consumed, and drug remaining. This reconciliation will be logged on the drug reconciliation

form, signed and dated. Any discrepancies noted will be investigated, resolved, and documented prior to return or destruction of the study drug.

11.9 Other Agent(s)

Not applicable

12. STUDY EVALUATIONS

12.1 Screening Phase

The screening phase will be up to 28 days. Screening is the interval between the signing of the informed consent form (ICF) and the day the subject receives the first dose of treatment in the study (Cycle 1 Day 1). Informed consent must be obtained before performing any study-specific procedures not considered standard of care. Assessments that are required to demonstrate eligibility may be performed over the course of 1 or more days during this phase.

Results from the screening visit evaluations will be reviewed to confirm subject eligibility before enrollment or the administration of study drug. Tests with results that fail eligibility requirements may be repeated during the screening phase if the investigator believes the results to be in error. Additionally, a subject who fails screening may repeat the screening process 1 time if the investigator believes there has been a change in eligibility status (eg, after recovery from an infection).

See **Section 13** for detailed list of screening procedures.

12.2 Treatment Phase

The treatment period will continue every 28 days and may continue as long as subjects are receiving benefit from treatment and have not met any criteria for study withdrawal.

See **Section 13** for list and schedule of procedures while on treatment.

12.2.1 Clinic Visits

During Cycle 1, patients will be seen every 2 weeks for vitals, physical exam, assessment of adverse effects, and appropriate laboratory tests and procedures (**Section 13**) Starting Cycle 2 and onward, patients will be seen on Day 1 of each cycle for vitals, physical exam, assessment of adverse effects, and appropriate laboratory tests and procedures. Patients may be seen for additional unscheduled visits as needed at the discretion of the investigator.

12.2.2 General laboratory assessment

See Section 13 for detailed laboratory tests and timing of these tests.

12.2.3 Schedule of Disease monitoring

A CT scan of the chest, abdomen, and pelvis with contrast will be obtained to evaluate disease status. A scan will be obtained at baseline (within 28 days of first study drug dose), then every 8 weeks for the first 32 weeks. After week 32, a CT chest, abdomen, pelvis with contrast will be performed every 12 weeks until disease progression, withdrawal from study, or ongoing disease control at 2 years (defined as at least stable disease at this point). For patients who achieve ongoing disease control at 2 years, subjects will be observed with a CT chest, abdomen, pelvis with contrast every 12 weeks. In patients who are unable to get a CT scan with contrast due to renal function (or any other reason), an MRI with and without contrast may be used instead. If the patient develops disease progression during this observation time, they will have the option of restarting study treatment at that time.

Table 7: Schedule of Disease Monitoring.

| | |
|--------------------------------------|---|
| Baseline scan | Baseline scan within 4 weeks prior to first treatment |
| Weeks 1 – 32 | Every 8 weeks +/- 1 week (at weeks 8, 16, 24, 32) |
| Weeks 33 – until disease progression | Every 12 weeks +/- 1 week (at weeks 44, 56, 68, 80, 92, 104) |
| 2 years | If subjects achieve ongoing disease control at 2 years, patients will be continued on study treatment and observed with imaging every 12 weeks +/- 2 weeks. |

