| Diagnosis and Main Inclusion Criteria | 
Main Inclusion Criteria:
 
 • Histopathologically confirmed diagnosis of metastatic advanced cutaneous squamous cell carcinoma. • History of solid-organ transplant requiring immunosuppression • Age ≥ 18 yrs • Measurable disease by RECIST v1.1 • KPS $\geq 60\%$, ECOG ≤ 2 • No prior JAK Inhibitor therapy • Adequate organ function • All clinically significant toxicities from prior systemic therapy must be \leq Grade 1 (with the exception of alopecia, and peripheral neuropathy, which may be \leq grade 2). • Subjects must agree to undergo tumor biopsies until biopsies have been obtained from 10 subjects (i.e., biopsies are required in at least the first 10 enrolled subjects, or until a goal of 10 study biopsies are obtained). Subjects in whom a biopsy is technically not feasible or in whom would result in unacceptable risk in the opinion of the investigator, may be exempted from the biopsy requirement with discussion with the principal investigator. • Negative pregnancy test for women of child bearing potential • Ability to take oral medications • Adequate marrow function: 
 - ANC ≥ 1000 /mm³ - Platelet count $\geq 50,000$/mm³ - Hemoglobin ≥ 8.0g/dL (not requiring transfusion in the past 2 weeks) |
| Study Product, Dose, Route, Regimen | Ruxolitinib will be administered orally twice daily during the entirety of each 28-day cycle. There will be a safety lead-in cohort of 6 patients who receive the starting dose of 15mg twice daily (BID). If dose limiting toxicities (DLT) are seen in 1 or fewer patients, the starting dose for all remaining patients will be 15mg BID. If DLT's are seen in >1 patient, another 6 patients will be enrolled at 10mg BID. If DLT's are seen in 1 or fewer patients, the starting dose for the remaining patients will be 10mg BID. Otherwise the study will be terminated. Individual subjects may have dose reductions of ruxolitinib during the course of treatment, based upon safety laboratory assessments. |

| | |
|-----------------------------------|---|
| Duration of administration | Treatment with ruxolitinib will commence following enrollment and continue until objective disease progression as confirmed by RECIST v1.1, intolerable toxicity or the occurrence of another discontinuation criterion. |

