5. STUDY DESIGN

5.1 General Design

This is an open-label, multi-center, Phase II study to evaluate the efficacy of ruxolitinib in post-transplant patients with advanced cutaneous squamous cell carcinoma.

Study Intervention: In a safety lead-in of 6 patients, subjects will receive ruxolitinib 15mg BID. After 4 weeks, if dose-limiting toxicities (DLT) are observed in 1 or fewer patients, the study will enter stage 1 of the Simon two-stage design where all subsequent patients will receive a starting dose of ruxolitinib 15mg BID. If more than 1 DLTs are observed, another cohort of 6 patients will be treated at a dose of 10mg BID. If less than 2 DLTs are observed at the new dose of 10mg, then the study will proceed to stage I using this dose; otherwise the study will stop.

Individual subjects may have dose reductions of ruxolitinib during the course of treatment, based upon safety laboratory assessments.

Schedule of Evaluations: Subjects will have regularly scheduled study visits at the clinical site on Day 1 and Day 15 (\pm 3 days) of the first cycle, then on Day 1 (\pm 3 days) of every subsequent cycle (starting cycle 2), where safety assessments, including laboratory assessments, vital signs, and physical examinations will be performed (see Section 12 for study calendar).

Response to treatment will be determined by CT scans of the chest, abdomen, and pelvis with contrast. The overall response rate for the primary endpoint evaluation will be determined by RECIST v1.1 criteria. In patients who are unable to get a CT scan w/ contrast due to renal function (or any other reason), an MRI with and without contrast may be used instead. Imaging will be performed at the following time points:

| | |
|--------------------------------------|---|
| Baseline scan | Baseline scan within 4 weeks prior to first treatment |
| Weeks 1 – 32 | Every 8 weeks +/- 1 week (at weeks 8, 16, 24, 32) |
| Weeks 33 – until disease progression | Every 12 weeks +/- 1 week (at weeks 44, 56, 68, 80, 92, 104) |
| 2 years | If subjects achieve ongoing disease control at 2 years, patients will be continued on study treatment and observed with imaging every 12 weeks +/- 2 weeks. |

Duration of treatment: Subjects will continue treatment until confirmed radiographic disease progression, intolerable toxicity or side effects (Section 6.5.1).

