8.5 Duration of Therapy

In the absence of treatment delays due to adverse events, treatment may continue for until one of the following criteria applies:

- Disease progression
- Intercurrent illness that prevents further administration of treatment
- Unacceptable adverse events(s)
- Patient decides to withdraw from the study
- General or specific changes in the patient's condition render the patient unacceptable for further treatment in the judgment of the investigator

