11.2 Treatment Regimen

Ruxolitinib is an orally-administered tablet. Patients with adequate hematologic counts will be started on a dose of 10mg twice daily. Dosing will be adjusted for safety as delineated. Treatment will consist of 28-day cycles. Treatment will continue until disease progression or severe toxicity requiring cessation.

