12.4.2 Follow-up (patients taken off treatment for reasons other than POD)

Subjects who discontinue study treatment for a reason other than disease progression (including patients who achieve stable disease control at 2 years) will move into the follow-up phase and will be assessed every 12 weeks by radiologic imaging to monitor disease status.

For patients who achieved stable disease at 2 years, re-treatment on study may be allowed at the time of disease recurrence or progression with permission of the study PI.

Every effort should be made to collect information regarding disease status until the start of new anti-neoplastic therapy, disease progression, death, and end of the study.

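### For patients with disease control at 2 years, section 5.1 and Table 7 continue ruxolitinib, while section 12.4.2 treats them as off drug and a restart at progression is offered

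*Combined protocol and SAP*

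**What the plan says.** Two places address the 2-year group directly and keep them on drug. Table 7 in section 12.2.3 reads "If subjects achieve ongoing disease control at 2 years, patients will be continued on study treatment and observed with imaging every 12 weeks", and the imaging table in section 5.1 says the same.

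The general duration rules contain no 2-year limit. Section 5.1 states "Subjects will continue treatment until confirmed radiographic disease progression, intolerable toxicity or side effects", and section 11.2 states "Treatment will continue until disease progression or severe toxicity requiring cessation". Section 12.2 lets treatment run for as long as the patient benefits and meets no withdrawal criterion. The synopsis has treatment "continue until objective disease progression as confirmed by RECIST v1.1, intolerable toxicity or the occurrence of another discontinuation criterion". Section 8.5 is permissive: "treatment may continue for until one of the following criteria applies".

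Two places point the other way. Section 12.4.2 deals with patients who stop for a reason other than progression and adds "including patients who achieve stable disease control at 2 years) will move into the follow-up phase". It then permits re-treatment on recurrence or progression if the study PI agrees. The narrative of section 12.2.3, directly above Table 7, describes patients with disease control at 2 years as being observed with scans every 12 weeks and says that on progression "they will have the option of restarting study treatment at that time".

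**The concern.** A drug can be restarted only if it has been stopped. The 12.2.3 narrative and section 12.4.2 both assume a stop at 2 years; the section 5.1 table and Table 7 order continuation. A site following Table 7 would keep dosing, and a site following 12.4.2 would stop. Both would be acting in good faith.

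At stake are drug exposure after 2 years and the monitoring tied to it. These are immunosuppressed transplant recipients, and section 10.1 warns of serious opportunistic infection on ruxolitinib, so whether they are on drug should not be left to interpretation. Scan timing, and with it the dating of late progression for PFS and duration of response, also depends on which status applies.

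**Working it through.** No sample size, power or event count depends on this point, so there is no figure of the plan to reproduce. The check is a comparison of text, followed by a look at what depends on it.

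**1. Is it the same group?** Section 12.2.3 defines disease control at 2 years as at least stable disease. Section 12.4.2 speaks of stable disease control at 2 years. On a plain reading these are the same patients.

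**2. What does each place instruct?**

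| Place | Drug after 2 years | Kind of statement |
|---|---|---|
| 5.1 imaging table | Continue | Explicit, specific to the 2-year group |
| Table 7 (12.2.3) | Continue | Explicit, specific to the 2-year group |
| 5.1 duration of treatment; 11.2 | Continue to progression or toxicity | General, no 2-year cap |
| 12.2 | Continue while benefiting | General, no 2-year cap |
| Synopsis; 8.5 | Continue, with room for another reason to stop | General, compatible with either reading |
| 12.4.2 | Stopped | Explicit, specific to the 2-year group |
| 12.2.3 narrative | Stopped, by implication of the restart | Specific to the 2-year group |

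**3. Does precedence settle it?** No. Letting a specific rule override a general one does not help, because there are specific statements on both sides. The conflict also sits inside section 12.2.3, between its text and its own table.

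**4. What depends on the status?**
- On drug, patients are seen on Day 1 of each 28-day cycle for adverse events and laboratory tests (12.2.1 and the study calendar): 52 weeks / 4 weeks = 13 visits a year.
- Off drug, routine adverse event reporting ends between 30 days (10.2) and at least 90 days (12.4.1) after the last dose: 30 / 28 = 1.1 cycles to 90 / 28 = 3.2 cycles.
- Imaging on drug is every 12 weeks +/- 2 weeks (Table 7). Off drug it is every 12 weeks in 12.4.2, but every 8 weeks +/- 1 week in 8.6 for patients off therapy for reasons other than death or progression.

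**5. What does not depend on it?** The primary endpoint is the best confirmed response in the first 24 weeks (17.2), and the two-stage rule counts those responses (17.1). Both are settled long before week 104.

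**6. How many patients?** Planned accrual is 35. A second safety lead-in adds 6, so the maximum is 35 + 6 = 41 (5.2, 17.1). The documents give no disease control rate at 2 years, so no estimate between 0 and that ceiling is possible.

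**The case against.** The best attempt to reconcile the text is that 12.4.2 covers only those 2-year patients who happen to stop for some other reason. Its wording does not carry that limit. The parenthetical names the group as a whole, and the re-treatment sentence addresses patients with stable disease at 2 years as a class.

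Other objections do stand, and they limit the point.

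- **Restart and the general rules.** A reader might infer a second contradiction, because 9.1 allows a cycle to begin only without progressive disease and 12.4.3 moves patients with confirmed progression to survival follow-up. The documents do not compel that reading. The permission in 12.4.2 names its patients, its trigger and who must agree, and can be taken as a specific rule to which the general ones yield. Section 6.5 can be read as covering only patients still on drug. What is missing is a cross-reference.
- **Option or permission.** A reader might also see a conflict between the patient's option in 12.2.3 and PI permission in 12.4.2. The two can coexist: the patient chooses and the PI must agree.
- **About half the trial.** Three sites at 1 patient every 2 months give 3 x 0.5 = 1.5 a month. If 36 months were a hard cut-off, (36 - 24) x 1.5 = 18 of 35 patients, or 51%, would be enrolled early enough to reach 2 years. That counts opportunity, not disease control. It also assumes on-target accrual with no pause after the lead-in and a cut-off that the documents do not state, so it should not be read as the number affected.
- **Lost safety data.** Section 10.3 keeps possibly related serious adverse events reportable after the study period, and lighter monitoring off drug is not in itself a defect. The difference between 30 and 90 days is a separate matter that does not arise from the 2-year conflict.
- **Intent.** The restart provision appears in two sections, so it may be deliberate. The documents do not show which rule the sponsor means.

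**Conclusion.** The point holds, and it is minor. The plan gives opposite instructions on whether patients with disease control at 2 years stay on ruxolitinib, and no other section resolves them. Drug exposure, Day 1 safety visits and scan timing after 2 years are left open. The primary analysis and the go/no-go decision are not affected.

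The size is unknown: somewhere from 0 patients up to a ceiling of 41. The conclusion rests on one reading, that the groups named in 12.2.3 and 12.4.2 are the same, which the definition in 12.2.3 supports.

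**What to change.** The sponsor should state one rule.

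**Default: continue**, which matches section 5.1, Table 7 and section 11.2.
- In 12.2.3, delete the sentence offering a restart at progression. State that patients with disease control at 2 years continue study drug, with imaging every 12 weeks +/- 2 weeks.
- In 12.4.2, delete the parenthetical about 2-year patients and the re-treatment sentence.

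This removes two sentences and one parenthetical and adds one sentence. Sample size and analyses do not change. Compared with Table 7 nothing is added. Compared with 12.4.2, the cost is continued Day 1 visits and drug supply for these patients, and they lose the re-treatment option.

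**Alternative: stop and restart**, if that is what the sponsor intends.
- Correct the 5.1 table and duration text, Table 7, the synopsis, 11.2 and 12.2.
- Add cross-referenced exceptions in 6.5, 8.5, 9.1 and 12.4.3.
- Align off-drug imaging between 8.6 (8 weeks) and 12.4.2 (12 weeks).
- State that restart needs PI permission.
- State that the first progression remains the PFS event, whatever happens on re-treatment.

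This route touches more sections but keeps the re-treatment option.

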12.2.4 Collection of Tumor Biopsies and Blood for Correlative Studies

A minimum of 10 subjects must undergo pre- and on-treatment research tumor biopsies. Subjects in whom biopsy is technically not feasible or in whom would result in unacceptable risk, in the opinion of the investigator, may be exempted from the biopsy requirement with discussion with the principal investigator. Use of outside archived tumor tissue for a baseline biopsy is not permitted. Biopsies will be collected at baseline and between C2D1 and C2D8 of therapy for correlative studies. An optional research biopsy at the time of progression will also be discussed with these patients, however, is not mandatory.

Whole blood will be requested as outlined in section 13.2 for peripheral blood mononuclear cell (PBMC) and circulating tumor DNA (ctDNA) collection to evaluate the effect of ruxolitinib on circulating immune cell populations before and during treatment and to further evaluate ctDNA as a potential biomarker of disease response.

12.2.5 Adverse Events Monitoring

Adverse events will be monitored from the time the subject receives the first dose of study treatment. Subjects will be instructed to report all AEs during the study and will be assessed for the occurrence of AEs throughout the study. All AEs (serious and nonserious) must be recorded on the source documents and eCRFs regardless of the assumption of a causal relationship with the study drug. The definition, reporting, and recording requirements for AEs are described in

Section 10.

All AEs of unknown etiology associated with ruxolitinib exposure should be evaluated to determine if it is possibly an irAE.

12.3 End of Treatment

If a decision is made that the subject will permanently discontinue study drug, the EOT visit should be conducted. If the EOT visit coincides with a regular study visit, the EOT evaluations will supersede those of that scheduled visit, and the data should be entered in the EOT page in the eCRF. The subject should be encouraged to return for the follow-up visits.

12.4 Follow-up Phase

12.4.1 Safety Follow-up

The safety follow-up phase is the interval between the last dose of study treatment and the scheduled safety follow-up visits, which should occur on days 30 (+/- 7 days) after the EOT visit. Adverse events and SAEs must be reported up until at least 90 days after the last dose of study drug, or until study drug-related toxicities resolve, return to baseline, or are deemed irreversible, whichever is longer. If a subject initiates a new anti-cancer therapy within 90 days after the last dose of study treatment, the next scheduled safety follow-up visit must occur before the first dose of the new therapy. Once new anti-cancer therapy has been initiated, the subject will move into the survival follow-up phase.

